### 10:7 Drop-outs and Missing Data

Drop-outs before day 7 of ICU stay will be considered as withdrawals. Drop-outs after that day will be evaluated in the primary outcome variable, and the same goes for day 10. For evaluation in length of stay and mortality, drop-out will be considered as withdrawals. Missing data will be considered as non-existent.

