Another problem is how to define morbidity and mortality. The latter is easily defined although the ICU mortality may be influenced by different routines in individual centres. In addition the beneficial effects attributable to nutritional support may be extended also to the convalescence and rehabilitation period and therefore 6-months mortality is considered a more adequate measurer than in unit or in hospital mortality. Concerning morbidity it may be reflected in the SOFA-score, which take failure in several organs into account (38). As there is a close correlation between SOFA-score and mortality, it may be the best integrated measure of morbidity. Morbidity of clinical importance it may also be reflected in the length of ICU-stay. It is obvious that ICU-stay is variable inbetween units as much as it depends upon the pressure on available ICU-beds and the quality of the post-ICU care. Hospitals with step down units may have quite different routines from those hospitals that lack such a facility. Although there will be considerable differences between units, a block-randomisation may at least to some extent take care of these problems. Still definition of morbidity is problematic, and to choose a measure of morbidity as a primary endpoint must always include a number of compromises.

In addition a close record of the nutrition given is also necessary to verify that the intended treatment is actually received by the patients. The record should include the energy given as well as nitrogen content.

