## 8:2 Secondary objectives

Mortality in the ICU and after discharge up to 6 months will be recorded and the cause of death will be registered. The difference in SOFA-score will also be calculated until day 10 of ICU stay according to the same procedure as for the primary objective under section 8:1. Length of ICU stay will also be recorded. If the patient is readmitted within 24 h after discharge the study continues. Readmission later than 24 h after discharge will not be recorded.

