#### 10:2 Secondary objectives

The 6-months mortality will be recorded from the public register. Mortality rates will be compared using a Kaplan-Meyer plot and ?-analysis. The change in SOFA score will be compared between groups using Student's t-test, as for the primary end-point.

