## 10:6 Subject classification

All patients who are eligible for the study are registered and if they are not randomised the reason is noted. All patients that are randomised are registered as randomised and as included if treatment is started. For patients who are randomised but not included the reason is noted. Patients who are randomised and have received treatment will be classified as withdrawals. Patients may withdraw from the trial at their own request or at the discretion of the investigator. Patients treated for less than 3 days (3 treatment periods) will also be classified as withdrawals. Patients with failure of treatment on two consecutive days will also be withdrawn from the study. A minimum of 3 treatment periods on consecutive days will be necessary for evaluation. Analyses of the results will be made on the basis of included patients as well as on the basis of "intention to treat" and "screened patients". "Intention to treat" meaning all patients randomised, including those not given 3 days of treatment depending upon death, discharge or discontinuation of other reasons. "Screened patients" meaning all patients possible to include.

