# 19:4 Patient report form

Discharge:

Serial number xxxxxx Day of discharge yyyy-mm-dd

Route of discharge: Step-down unit Ordinary ward Another hospital/ICU Dead Other way

Drop out: Y/N

Withdrawn consent Failure of drug administration Other reason

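### On its plain reading, section 10:7 takes drop-outs out of the mortality and length-of-stay analyses, contradicting the intention-to-treat analysis promised in sections 10 and 10:6

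*Protocol*

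**What the plan says.** Section 10:7 sets the rule for these two endpoints: "For evaluation in length of stay and mortality, drop-out will be considered as withdrawals". It names no analysis set and makes no exception. For the SOFA endpoints it works by date. Drop-outs before day 7 are withdrawals, and then: "Drop-outs after that day will be evaluated in the primary outcome variable, and the same goes for day 10". The section ends with "Missing data will be considered as non-existent".

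Drop-out can arise in several ways. Section 10:6 allows withdrawal at the patient's request or at the investigator's discretion, and adds: "Patients with failure of treatment on two consecutive days will also be withdrawn from the study". The report form in 19:4 offers three reasons: withdrawn consent, "Failure of drug administration", and other.

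Outcome collection does not depend on continuing study drug. Section 10:2 says "The 6-months mortality will be recorded from the public register", and 8:2 says "Mortality in the ICU and after discharge up to 6 months will be recorded and the cause of death will be registered". Section 9:2 has deaths in randomised patients reported as serious adverse events. Section 8 records when the ICU stay ends and how the patient was discharged.

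The opening of section 10 has all calculations done on included patients and on randomised patients. Section 10:6 defines intention to treat as everyone randomised, including those who stopped before three days for any reason. It also lists analyses of included and of screened patients. None of these sets is called primary.

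**The concern.** Drop-out happens after randomisation. Stopping study drug does not make vital status unknown when deaths come from a register. If drop-outs leave the mortality analysis, known deaths are set aside and the groups compared are no longer those that were randomised.

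The Background (section 3) holds that "6-months mortality is considered a more adequate measurer than in unit or in hospital mortality", so the rule touches the outcome the protocol regards as the better mortality measure. For length of stay, 10:5 plans a rank test that places deaths below survivors, so removing drop-outs who died also removes known low ranks.

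The protocol also supports two different mortality results, one following 10:7 and one following the intention-to-treat text, without saying which is the main one. That choice should not be open once results can be seen.

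**Working it through.** **What 10:7 means.** Within 10:7, being a withdrawal is set against being evaluated. Section 10:6 likewise classes patients with fewer than three treatment periods as withdrawals and requires three for evaluation. On that usage, a drop-out is not evaluated for mortality or length of stay. There is no date cut-off here, so a patient who drops out after day 7 counts for the SOFA change but not for mortality.

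**What would be known about a drop-out.**
- 6-month vital status: yes, from the register (10:2), unless consent to that follow-up is withdrawn.
- Death: reported for randomised patients (9:2).
- Stay in the study ICU: yes (section 8). Total ICU stay after transfer to another unit: not necessarily, because section 8 says that such a patient leaves the study.

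**Plan's own figures.** None is given for mortality, length of stay or drop-out. The only number used below is 500 per arm (6:5). It was sized on SOFA change, and 10:3 gives neither SD nor alpha, so it cannot be reproduced; nothing here depends on it.

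**Illustration; every rate is an assumption.** Take no treatment effect, true mortality m in both arms, drop-out proportion d and mortality q among drop-outs. Mortality after exclusion is (m − d·q)/(1 − d), and deaths removed per arm are 500·d·q.

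Worked case, m = 30% (150 deaths per arm), q = 60%:
- d = 10% in both arms: (150 − 30)/(500 − 50) = 120/450 = 26.7% in each. 60 of 300 deaths are removed and the difference is zero.
- d = 8% v 12%: (150 − 24)/460 = 126/460 = 27.4%, and (150 − 36)/440 = 114/440 = 25.9%. Again 60 of 300 deaths are removed; the false difference is 1.5 points. Pooled proportion 240/900 = 0.267; SE = √(0.267 × 0.733 × (1/460 + 1/440)) = 2.9 points; the shift is 0.5 SE. A nominal 5% two-sided test then rejects about 8% of the time.

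The range, with differences taken before rounding:

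| m | drop-out | q | deaths removed | observed mortality | false difference | rejection rate (nominal 5%) |
|---|---|---|---|---|---|---|
| 30% | 5% v 15% | 30% | 30 of 300 | 30.0% v 30.0% | 0 | 5% |
| 30% | 5% v 15% | 50% | 50 of 300 | 28.9% v 26.5% | 2.5 points | 13% |
| 20% | 5% v 15% | 50% | 50 of 200 | 18.4% v 14.7% | 3.7 points | 32% |
| 30% | 10% v 20% | 60% | 90 of 300 | 26.7% v 22.5% | 4.2 points | 29% |
| 20% | 10% v 20% | 60% | 90 of 200 | 15.6% v 10.0% | 5.6 points | 67% |

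Equal frequency with unequal prognosis also shifts the comparison. At m = 30%, d = 10% in both arms and q = 30% v 50%, the result is 135/450 = 30.0% v 125/450 = 27.8%, a false 2.2 points.

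**Precision.** If drop-out is unrelated to prognosis, power for 30% v 22% mortality at two-sided 5% is 82% with 500 per arm, 78% with 450 and 73% with 400.

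**The case against.** The best defence is that 10:7 only classifies. It does not say that withdrawals are removed from every analysis. Section 10:6 classes patients treated for less than three days as withdrawals and still counts them under intention to treat, and section 10 applies both sets to every calculation. Read together, drop-outs could remain in an intention-to-treat mortality analysis. This part stands: a reader might infer that the protocol definitely discards known deaths throughout, and the text does not establish that. But 10:7 is the endpoint-specific rule, it carries no exception, and nothing says which analysis leads. The contradiction remains.

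A reader might also infer that drop-out tracks severity, so that the mortality comparison is bound to be biased. No section says so. A failed infusion may be purely logistical, and blinding with products of the same appearance (5:3) makes unequal drop-out less likely. The modest 8% v 12% case raises the false-positive rate only to about 8%; the large errors need much wider imbalances, which nothing in the protocol suggests.

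Length of stay is not known as fully as vital status. Section 8 ends study participation on transfer to another ICU, although it keeps patients treated for more than three days in the evaluation. Finally, these are secondary endpoints, and the sentence leaves the primary test untouched.

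**Conclusion.** The point holds as a contradiction with a harmful plain reading. Section 10:7 excludes drop-outs from mortality and length of stay after randomisation, sections 10 and 10:6 promise an analysis that keeps them, and no set is primary. Following 10:7 could discard known deaths.

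The size cannot be computed from the protocol. If drop-outs die more often than the others (an assumption), mortality is understated. In the absence of a treatment effect, a false difference between arms arises only if drop-out differs between arms in frequency or prognosis; unequal frequency alone does no harm when drop-outs have the same mortality as everyone else. Otherwise the cost is mainly lost deaths and precision. The conclusion is firm for mortality and weaker for length of stay, where only the stay in the study ICU can be relied on.

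**What to change.** Replace the sentence in 10:7 with text such as: *The primary analysis of ICU mortality, 6-month mortality and length of stay in the study ICU includes all randomised patients in their assigned arm, whether or not study drug was stopped. Any analysis that excludes drop-outs is supportive only.*

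Add a rule for patients who withdraw consent to register follow-up. In the Kaplan-Meier analysis, and in a log-rank test if one accompanies it, they are censored at the date of withdrawal. The chi-square comparison in 10:2 and 10:5 cannot use censored observations, so for that test and for length of stay the number of such patients per arm is reported, with a best-case and worst-case sensitivity analysis.

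The cost is a few lines of text. The register look-up, death reports and discharge records are already planned, and the sample size does not change. The change should be settled before any unblinded comparison, preferably before the interim analysis at 500 patients.

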#### 11. Study co-ordinator

A study co-ordinator will support the study and register all the electronic reports. Investigators not reporting daily will be contacted to inquire whether they need any type of support. Whenever daily reports are not complete or any other question arises, study coordinator will also contact the investigator. Study co-ordinator will also help to see that study drug is available in sufficient amounts at the local Pharmacies at the participating centres.

#### **12. Quality control**

The principal investigator or country responsible investigator will together with the study coordinator visit participating centres to help local investigators to have uniform routines, uniform data collection and to assure storage of the signed paper copies of case report files.

#### **13. Stopping rules**

After recruitment of 200 patients a check up will be done in order to see that the protocol is functional and that the recruitment is sufficient to complete the study within the expected time. After 500 patients a interimistic calculation a difference in the primary endpoint between the two treatment groups will be made. A decision will then be taken whether to continue or not.

#### 14 Ethics

As glutamine supplementation of nutrition is not evaluagted in a prospective double-blinded placebo-controlled multi-centre trail in ICU patients this needs to be done. The protocol is in accord with the Declaration of Helsinki.

## 14:1 Ethics approval

Ethical permission will be applied for separately in the participating countries. In Sweden Ethics Committees of all universities should be approached simultaneously, while in Denmark, Finland and Norway the procedure starts at one university.

#### 14:2 Regulatory approval

Permission from national regulatory authorities will be applied for in each participating country.

## 15. Documentation and record keeping

#### 15:1 Case Report Form

Data will be reported electronically and a special case report form will be designed for the report (Appendix 8.5). The study co-ordinator will check the input from the different centres on a daily basis and immediately make contact when reporting fails.

#### 15:2 Data management

Signed paper copies of the case report forms will be kept at the participating centres. All electronically submitted case report forms will be stored electronically, and patients will only be identified by their 6-digit trail number.

#### 15:3 Record retention

The case report forms will be stored safely at the local centres for 3 years. The electronic data-filfes will be stored safely by principal investigator for 5 years.

## **16. Reporting and publication**

As the study is a part of the activities of the Scandinavian Critical Care Trails Group, it will be reported and published in the name of the Network. Accompanying studies using the protocol of the multi-centre study and adding other investigational parameters are encouraged. Such extensions may then give reference to the multi-center study and Scandinavian Critical Care Trails Group when publishing. As the study is an investigators trail, without any industrial sponsor, publication of the results is at the discretion of the principal investigator and the steering group of the study within the framework of the Scandinavian Critical Care Trails Group.

## **19. Appendages**

19:1 SOFA-score table

19:2 Harris-Benedict table

19:3 Dosage table

19:4 Electronic report form

## 19:1 SOFA-score

SOFA -score	1	2	3	4
Respiration PaO 2 /FiO 2 , mmHg	300-399	200-299	100-199	<100
(kPa)	(40.1-53.3)	(26.8-40.0)	(13.3-26.7)	(<13.3)
Coagulation Platlets x10  /mm 	100-140	50-99	20-49	<20
Liver Bilirubin, mg/dl	1.2-1.9	2.0-5.9	6.0-11.9	>12.0
(µmol/l)	(20-32)	(33-101)	(102-204)	(>204)
Cardiovascular				
Hypotension	MAP <70 mmHg	Dopamine ≤ 5 a or dobutamine (any dose)	Dopamine >5 or epinephrine $\leq 0.1$ or norepinephrine $\leq 0.1$	Dopamine>15 or epinrphrine >0.1 or norepinephrine >0.1
Central nervous system Glasgow Coma Scale	13-14	10-12	6-9	<6
Renal Creatinine, mg/dl (μmol/l) or urinary output	1.2-1.9 (110-170)	2.0-3.4 (171-299)	3.5-4.9 (300-499) or <500ml/day	>5.0 (>440) or<200ml/day

a Adrenergic agents administered for at least 1h (doses given are in  $\mu$ g/kg  $\cdot$  min)

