### 6:1 Screening

Screening will be performed when it is decided to prescribe full nutrition to the patient, usually during the initial 2 days of ICU-stay before the trial starts. During the screening following tasks will be performed.

- a) Detailed patient/relative information by the investigator and handout of the written patient/relative information
- b) List of inclusion/exclusion criteria will be checked
- c) Subject's demographic data will be controlled

Recording of APACHE II score at admission (during first 24 h of stay)

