#### 8:1 Primary objective

The difference in SOFA-score will be calculated from the day starting nutritional treatment as well as glutamine supplementation until day 7 of ICU stay. For patients discharged or dead before day 7, the SOFA score on the day of discharge/death will substitute the latter score. In case of restrictions in treatment, SOFA score will be recorded as long as the nutrition of the patient is maintained.

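### The renal SOFA item takes no account of renal replacement, so starting dialysis in a non-oliguric patient can enter the primary endpoint as a 3-4 point improvement

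*Protocol*

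**What the plan says.** Protocol 19:1 defines the renal row by creatinine "or urinary output". The score 3 cell is "3.5-4.9 (300-499) or <500ml/day" and the score 4 cell is ">5.0 (>440) or<200ml/day". Creatinine of 110-170 µmol/l scores 1; anything lower falls below the first printed band and so scores 0.

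The cardiovascular row works differently. From score 2 upwards it is defined by the drugs given and their dose, and the table's only footnote concerns that row: "Adrenergic agents administered for at least 1h". The table has no corresponding rule for renal support. Dialysis and renal replacement are also absent from the exclusion criteria (6:3), the daily task list (8) and the endpoint rules (8:1, 8:2).

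The score feeds directly into the primary endpoint. Under 8:1, "The difference in SOFA-score will be calculated from the day starting nutritional treatment as well as glutamine supplementation until day 7 of ICU stay". When a patient leaves or dies earlier, "the SOFA score on the day of discharge/death will substitute the latter score". Section 8:2 applies the same procedure to day 10. Section 10:3 sizes the trial for a 0.75-point difference in this change, with 80% power and about 500 patients per group.

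**The concern.** Dialysis lowers creatinine by clearing it, so a lower value on dialysis does not show that the kidney has recovered. A table that reads only creatinine and urine cannot tell the two apart. If a patient's renal failure is severe enough for dialysis to be started between baseline and day 7, and urine volume is preserved, the printed rule records an improvement where the clinical course was an escalation of organ support. The sign of that patient's renal contribution is then wrong.

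The table is also inconsistent with itself. A patient whose blood pressure is held up by norepinephrine is scored for the norepinephrine, whereas a patient whose creatinine is held down by dialysis is scored as if no support were given.

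This cannot safely be left to an analysis plan. Sites calculate SOFA daily (section 8), and 5:4 makes the report form the primary data. If renal replacement is not recorded at the time, the correct score may not be recoverable later.

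**Working it through.** **1. Applying the printed limits.** The renal score is taken as the worse of the creatinine and urine criteria. Creatinine 520 µmol/l is used because it lies clear of the 441-499 range, where the printed bands for 3 and 4 overlap (a separate matter that needs reconciling).

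| Urine (ml/day) | Before dialysis | On dialysis | Recorded change |
|---|---|---|---|
| 800 | creatinine 520: 4 | creatinine 150: 1 | 3-point improvement |
| 800 | creatinine 520: 4 | creatinine 100: 0 | 4-point improvement |
| 800 | creatinine 430: 3 | creatinine 100: 0 | 3-point improvement |
| 300 | creatinine 520: 4 | creatinine 100, urine scores 3: 3 | 1-point improvement |
| 100 | creatinine 520: 4 | creatinine 100, urine scores 4: 4 | none |

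The large artefact therefore needs high creatinine, urine of at least 500 ml/day and dialysis started after baseline.

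**2. The plan's own figure.** Section 10:3 states no SD, and the protocol gives no significance level or sidedness, so 500 per group cannot be reproduced independently. Solving backwards with two-sided 0.05 (assumed) and 80% power:

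SD = 0.75 / [(1.960 + 0.842) × √(2/500)] = 4.23

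One-sided 0.05 would give 4.77. With 4.23, the standard error of the difference is 4.23 × √(2/500) = 0.27. Any adjustment for the interim analysis is ignored.

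**3. Same share affected in both arms (noise).** Let p be the assumed share of patients with a 4-point artefact that is independent of the rest of the change. Then SD_new = √(4.23² + 4² × p(1 − p)).

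| p | SD | Power at 500 per group | n per group for 80% |
|---|---|---|---|
| 0 | 4.23 | 80% | 500 |
| 5% | 4.32 | 78% | 522 |
| 10% | 4.40 | 77% | 541 |
| 20% | 4.53 | 75% | 572 |

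**4. Different shares in the two arms (bias).** Shift = arm difference in share × points per patient.

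- 3 percentage points × 3 points = 0.09, which is 12% of 0.75 and 0.09/0.27 = about one third of a standard error.
- 5 percentage points × 3 to 4 points = 0.15 to 0.20, which is 20-27% of 0.75; 0.20/0.27 is about three quarters of a standard error.
- To produce the whole 0.75 target, the arms would have to differ by 0.75/4 = 19 to 0.75/3 = 25 percentage points.

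Every share in steps 3 and 4 is an assumption. The protocol gives no rate of dialysis, oliguria or discharge.

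**The case against.** The strongest reply is that the affected group is narrow. The urine criterion already keeps oliguric and anuric patients at 3 or 4, and nothing in the protocol says how many patients start dialysis with preserved urine output. In a randomised, double-blind trial an artefact that is equally common in both arms costs only a little power. This stands, and it limits the size of the point. It does not remove the point, because the rule as printed gives the wrong sign for these patients without any error by the site.

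A second reply is that the table follows a published score and should not be altered. The cost is real, but it is small and can be declared.

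A third is that the daily form may already record renal replacement. That cannot be ruled out: 19:4 shows only the discharge part, and 15:1 says a form is still to be designed. So a missing field cannot be asserted, and the protocol gives no scoring rule that would use one.

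A reader might infer two stronger points, which the document does not support:

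- **Part-day urine.** One might argue that a short start, discharge or death day makes normal urine flow look like oliguria. But the printed limits are volumes per day, that is, rates. An assumed flow of 60 ml/h is 60 × 24 = 1,440 ml/day however few hours are charted. Section 8:1 refers to the day of discharge or death without defining a midnight-to-midnight day, and 6:1 places screening "usually during the initial 2 days of ICU-stay before the trial starts", so many patients have earlier ICU hours charted. Reading a raw part-day total against a daily limit would be a site's misreading.
- **Bias in favour of glutamine.** One might argue that the extra nitrogen in the active arm leads to more dialysis and so to lower scores. The protocol offers no evidence that it does.

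**Conclusion.** The point holds for renal replacement only. Applied as printed, the renal item records a 3-4 point improvement when a non-oliguric patient with high creatinine starts dialysis after baseline, and that value enters both the primary endpoint and the day 10 endpoint. For one patient this is 4 to 5.3 times the target mean difference (3/0.75 and 4/0.75). For the trial the effect is much smaller, because only some patients can be affected.

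If the arms do not differ, the consequence is noise: power of 78% to 75% instead of 80% for assumed affected shares of 5-20%. An assumed arm difference of 3 to 5 percentage points shifts the estimate by about 0.09 to 0.20 points, favouring whichever arm has more such patients. The direction cannot be predicted from the document. The trial-level figures rest on these assumed shares, and those expressed as power, sample size or standard errors also on the back-solved SD of 4.23. The patient-level result rests on the printed table alone. The correction is worth making because the rule is wrong for the patients it affects and the remedy is cheap.

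**What to change.** Add a footnote to 19:1 stating that the renal item is scored 4 on any day with renal replacement therapy, whatever the creatinine or urine volume. The footnote should also say how days between intermittent sessions are scored, since day 7 or the day of discharge may fall on one. Make sure the daily form records renal replacement as yes or no, so that the rule can be applied and checked. If wanted, a short note can confirm that the urine limits refer to a 24-hour rate. Urine should not be ignored when fewer than 24 hours are charted: a patient anuric for 20 hours with still-normal creatinine would then score 0.

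The cost is one footnote and, if the form lacks it, one daily checkbox. The change concerns scoring only and leaves patient management untouched. The drawback is that the score departs slightly from the printed table, and patients on dialysis cannot show renal improvement until it stops.

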## 4:1 Primary objective

The primary objective is to compare the change in SOFA-score (Appendix 8:2) on day 7 of ICU stay as compared to the day starting nutritional treatment and glutamine supplementation. Only patients who have received glutamine for not less than 3 days will be considered.

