## 8. Efficacy assessment

Each day of the study following things will be performed:

a) study drug (glutamine or placebo) will be given intravenously during 12 h.

b) volume of infused solution and time interval of infusion will be registered.

c) total amount of nutrition during 24 h will be recorded.

d) SOFA score will be calculated.

End of ICU-stay will be recorded and as well as the route of discharge. If the patient is moved to another intensive care unit, the patient leaves the study. Still if the patient is treated more than 3 days, he is included and evaluated in the study although the ICU-stay is prolonged in another unit and patient during that time does not receive any controlled treatment. Provision of nutrition after ICU-stay (or after readmission to ICU) will not be recorded. If patient is readmitted to ICU within 24 h study protocol is continued. If patient is readmitted to ICU after more than 24 h the patient will not be included. Patient will not be included again in the study and the second (or consecutive) stay will not be recorded as ICU-stay in the protocol.

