#### 10:3 Sample size

The sample size is calculated to enable detection of a 0.75-point difference in change in SOFA-score after 7 days of treatment with 80% statistical power is based upon parametric statistics. In particular a limited effect during a short treatment period was taken into considerations. The choice of change in SOFA score was partly done on account that it can be assumed to be neutral to a non-identical The sample size of approximately 500 patients in each group are needed under these assumptions.

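### In the SOFA table (Protocol 19:1), creatinine above 440 up to 499 micromol/l meets both renal score 3 and renal score 4: a minor error in the primary endpoint's scoring table

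*Protocol*

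**What the plan says.** Section 4:1 makes the SOFA score the basis of the primary endpoint: "The primary objective is to compare the change in SOFA-score" between the start of treatment and day 7 of ICU stay. Section 8:1 substitutes the score on the day of discharge or death for patients who leave earlier. Section 8:2 applies the same procedure to day 10 as a secondary outcome. Section 8 lists, for each study day, that "SOFA score will be calculated".

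The scoring table is in section 19:1. Its renal row gives each creatinine band in mg/dl with micromol/l in brackets. Score 1 is 1.2-1.9 mg/dl (110-170 micromol/l) and score 2 is 2.0-3.4 mg/dl (171-299 micromol/l). Score 3 is "3.5-4.9 (300-499) or <500ml/day" and score 4 is ">5.0 (>440) or<200ml/day". The protocol does not say which unit governs, or which score to take when a value meets two definitions.

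**The concern.** A scoring table should give one score for each observation. Here a creatinine of, say, 460 micromol/l lies inside the closed band for score 3 and also above the threshold for score 4. Section 10:4 plans 20 centres in four countries, so different scorers may settle this differently. One scorer may also settle it differently at the start of treatment and on day 7, which would record a one-point change that did not occur. The conflict arises only when creatinine is read in micromol/l and urine output does not already fix the renal score. What is at stake is the reproducibility of one item of the primary endpoint.

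**Working it through.** **Overlap.** Score 3 covers 300 to 499 micromol/l and score 4 covers values above 440. The whole numbers that meet both run from 441 to 499, which is 499 − 441 + 1 = 59 values. Exactly 440 is score 3 only. The lower bands adjoin without overlap (170/171 and 299/300). In mg/dl, score 3 ends at 4.9 and score 4 is above 5.0, so there is no overlap.

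**Which figure is out of line.** Dividing each micromol/l limit by its mg/dl limit gives the conversion factor that the table itself implies:

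| Limit | Calculation | Factor |
|---|---|---|
| Score 1 lower | 110 / 1.2 | 91.7 |
| Score 1 upper | 170 / 1.9 | 89.5 |
| Score 2 lower | 171 / 2.0 | 85.5 |
| Score 2 upper | 299 / 3.4 | 87.9 |
| Score 3 lower | 300 / 3.5 | 85.7 |
| Score 3 upper | 499 / 4.9 | 101.8 |
| Score 4 threshold | 440 / 5.0 | 88.0 |

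Six of the seven lie between 85.5 and 91.7; only 499 / 4.9 does not. At those factors, 4.9 mg/dl is 4.9 × 85.5 = 419 to 4.9 × 91.7 = 449 micromol/l, and at 88.0 it is 431. In the other direction, 499 micromol/l is 499 / 91.7 = 5.4 to 499 / 85.5 = 5.8 mg/dl, which the table's own mg/dl limits place in score 4. So 499 is the figure in error, and the 440 threshold agrees with the rest of the row.

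**Size of the effect on the primary comparison.** Section 10:3 plans for "detection of a 0.75-point difference in change in SOFA-score after 7 days of treatment with 80% statistical power" with about 500 patients per group. It states neither the SD nor the significance level, so the sample size cannot be reproduced. Assuming two-sided alpha 0.05 and ignoring the interim adjustment, the implied SD is 0.75 × √(500/2) / (1.960 + 0.842) = 4.23.

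The documents do not give the share of patients with creatinine in the band. Take an assumed share q whose renal item is scored 3 or 4 at random, with equal chance, at both time points. Each random score has variance 0.25, so the change gains a variance of q × 0.25 × 2:

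| Assumed share q | SD of change | Power, 500 per group |
|---|---|---|
| 0 | 4.233 | 80.0% |
| 2% | 4.234 | 80.0% |
| 5% | 4.236 | 79.9% |
| 10% | 4.239 | 79.9% |

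**An extreme case.** If 5% of one arm were shifted by a full point and nobody in the other, the difference in mean change would move by 0.05 × 1 = 0.05 points. The design gives no reason to expect this. Treatment is double-blind (sections 5 and 5:3), and allocation is balanced within each centre (section 6:5), so a centre's scoring habit falls on both arms.

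**The case against.** The strongest reply is that the table can be read only one way. Its urine limits nest (below 500 and below 200 ml/day), and so do its dopamine limits (above 5 and above 15). Both work only if the highest criterion met counts. Read that way, creatinine of 441 to 499 scores 4, which is also what the corrected table would give. This is a plausible reading and many scorers would follow it. But the protocol nowhere states it, and the nested limits are open-ended whereas 300-499 is a closed band with an explicit upper limit. A scorer who looks at that cell alone is told that 499 is a 3.

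It is also fair to say that scorers working in mg/dl never meet the conflict, and that a urine output below 200 ml/day gives score 4 whatever the creatinine. Both points stand and narrow the set of affected days.

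A slip in the copy of the table at hand cannot be excluded, though nothing suggests one. A look at the master copy settles it.

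A reader might go further and infer that a one-point error exceeds the 0.75 points the trial is sized to detect, and so endangers the primary result. The documents do not support that. The one point is an error in a single patient's score, whereas 0.75 is a difference between group means. A reader might also put a number on the patients affected, but the protocol gives no creatinine distribution, so any such count restates an assumption.

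**Conclusion.** The inconsistency is real and can be checked from one row of the table: creatinine above 440 up to 499 micromol/l has two scores, and 499 contradicts its own 4.9 mg/dl. It belongs in a correction because the table produces the primary endpoint and the day-10 outcome. Its importance is minor. A single change score can be wrong by a point, but the expected result is slight non-differential noise, with no bias between arms and no material loss of power. That rests on blinding and within-centre balance holding as planned, and on the assumed alpha, SD and share of 2-10%. An effect on organ failure free days should not be inferred, since the Summary names that outcome without giving a threshold.

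**What to change.** In section 19:1, change the micromol/l range for renal score 3 from 300-499 to 300-440. It then adjoins the existing threshold for score 4 and agrees, within the row's own rounding, with 3.5-4.9 mg/dl. Build the same limits into the electronic form. If data have already been entered, re-score under blinding every day with creatinine above 440 up to 499 micromol/l, taking urine output into account.

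The cost is one table entry and one edit check. Re-scoring needs the creatinine value. The part of the report form shown in 19:4 does not reveal whether it is captured; if it is not, days with a renal score of 3 or 4 would have to be checked against the patient's chart.
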